#### Scenarios:

A. When the bcl-2 status is known before therapy (i.e., those patients who are not randomized -- see section 5.1.1):

- course 1: CHOD-Bleo, plus rituximab d. 1 & 8
- course 2: ESHAP
- course 3: NOPP, plus rituximab d.1 & 8
- course 4: CHOD-Bleo, plus rituximab d.1 only
- course 5: ESHAP
- course 6: NOPP, plus rituximab d.1 only
- courses 7-9: CHOD-Bleo; ESHAP; NOPP (No more rituximab)

B. If patient had been randomized, and got FND with rituximab:

- course 1: FND + rituximab d. 1 & 8
- course 2: CHOD-Bleo, plus rituximab d.1 & 8
- course 3: ESHAP
- course 4: NOPP, plus rituximab d.1 & 8
- course 5: CHOD-Bleo without rituximab
- course 6: ESHAP
- courses 7-9: NOPP; CHOD-Bleo; ESHAP (No more rituximab)

C. If patient had been randomized, and got FND without rituximab:

- course 1: FND
- course 2: CHOD-Bleo, plus rituximab d. 1 & 8
- course 3: ESHAP
- course 4: NOPP, plus rituximab d. 1 & 8
- course 5: CHOD-Bleo, plus rituximab d. 1 & 8
- course 6: ESHAP
- courses 7-9: NOPP; CHOD-Bleo; ESHAP (no more rituximab)

For any questions about this sequence, consult P.I.

For all cycles given in conjunction with rituximab, the steroid will start on d. 1 along with the rituximab, and the remainder of the chemotherapy will start one day later than standard, analogous to the modified schedule of FND as outlined in Section 5.

II. ATT doses and schedule (with rituximab in CHOD-Bleo and NOPP courses):

1. Initial Dosing Regimen for CHOD-Bleo:

Agent	Dose	Days	Route	Time	Total Dose
Rituximab	375 mg/m 	1 & 8	IV	approx 4 hr (Sec 5. 4)	750 mg/m 
Adriamycin	25 mg/m  /day	2-3	IV-CI	48 hrs	50mg/m 
Oncovin	0.7 mg/m  /day	2-3	IV-CI	48 hrs	1.4 mg/m 
Bleomycin	5 u/m  /day	2-3	IV-CI	48 hrs	10 u/m 
Cytosan	750 mg/m 	2	IVPB	15 min	750 mg/m 
Dexamethasone	40 mg/day	1-4	p.o.	--	160 mg

2. Initial Dosing Regimen for ESHAP:

Agent	Dose	Days	Route	Time	Total Dose
Etoposide	40 mg/m  (daily)	1-4	IV	30 min	160 mg/m 
Cisplatin	25 mg/m  (daily)	1-4	IV-CI	96 hrs	100 mg/m 
Ara-C	1.5 gm/m  (single dose)	5	IV	2 hrs	1.5 gm/m 
Solu Medrol	500 mg (daily)	1-5	IV	15 min	2500 mg

3. Initial Dosing Regimen for NOPP:

Agent	Dose	Days	Route	Time	Total Dose
Rituximab	375 mg/m 	1 & 8	IV	approx 4 hr (Sec 5.4)	750 mg/m 
Novantrone	10 mg/m  (single dose)	2	IV	15 min	10 mg/m 
Oncovin	1.4 mg/m 	2	IVPB	15 min	1.4 mg/m 
Procarbazine	100 mg/m 	2-11	p.o.	--	1000 mg/m 
Prednisone	100 mg	1-5	p.o.	--	500 mg

III. Dose modifications related to myelotoxicity.

1. For CHOD-Bleo

Dose Level:	-2	-1	0	1
Adriamycin ( total dose)	35 mg/m 	40 mg/m 	50 mg/m 	60 mg/m 
Cytosan	500 mg/m 	600 mg/m 	750 mg/m 	1000 mg/m 
Oncovin ( total dose)	1.4 mg/m 	1.4 mg/m 	1.4 mg/m 	1.4 mg/m 
Bleomycin ( total dose)	10 u/m 	10 u/m 	10 u/m 	10 u/m 
Dexamethasone (daily dose)	40 mg	40 mg	40 mg	40 mg

2. For ESHAP

Dose Level:	-2	-1	0	1
Etoposide (daily dose)	25 mg/m 	30 mg/m 	40 mg/m 	50 mg/m 
Cisplatin (daily dose)	16 mg/m 	20 mg/m 	25 mg/m 	25 mg/m 
Ara-C x1	0.5 mg/m 	1 g/m 	1.5 mg/m 	2 g/m 
Solu Medrol (daily dose)	500 mg	500 mg	500 mg	500 mg

3. For NOPP

Dose Level:	-2	-1	0	1
Novantrone	6 mg/m 	8 mg/m 	10 mg/m 	12 mg/m 
Oncovin	1.4 mg/m 	1.4 mg/m 	1.4 mg/m 	1.4 mg/m 
Procarbazine (daily dose)	60 mg/m 	80 mg/m 	100 mg/m 	120 mg/m 
Prednisone (daily dose)	100 mg	100 mg	100 mg	100 mg

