## APPENDIX B

### MANAGEMENT STRATEGY FOR FOLLICULAR LYMPHOMA PATIENTS WHO DO NOT HAVE BCL-2 MBR OR MCR GENE REARRANGEMENT ("GERMLINE" PATIENTS).

- I. Since these patients appear to have an inferior outcome with FND compared courses to ATT, these patients will receive ATT, 9 courses total, and all will also receive rituximab, 6 doses total. This will include d.1 and 8 doses of rituximab during the first cycles of CHOD-Bleo and NOPP (but not ESHAP) courses, and d.1 only during the second cycles of CHOD-Bleo and NOPP.

All "germline" patients will also receive interferon maintenance, as outlined for FND + rituximab patients (see 5.7).

Since the bcl-2 status may not be available prior to starting therapy, some will have received one (or rarely two) cycles of FND, with or without rituximab, prior to crossover to ATT. In such cases, the final chemotherapy cycle of the ATT sequence (NOPP) will be omitted, so that the total number of chemotherapy cycles is nine.

If the patient had been randomized to receive FND + rituximab and thus already received doses of rituximab, the subsequent courses of ATT, with d.1 and 8 IDEC during each CHOD-Bleo and NOPP course, should complete all 6 planned doses of rituximab (see scenario B below). For any patient who does not complete nine courses of chemotherapy, any missed doses of rituximab can be completed after the last chemotherapy cycle.

If the patient had been randomized to receive FND without rituximab, see scenario C.

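### Appendix B plans six rituximab doses for germline patients, but one sentence and the Part II dosing tables do not agree with that plan course by course

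*Combined protocol and SAP*

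**What the plan says.** Appendix B, Part I, says that "these patients will receive ATT, 9 courses total" and that "all will also receive rituximab, 6 doses total". It places those doses as "d.1 and 8 doses of rituximab during the first cycles of CHOD-Bleo and NOPP (but not ESHAP) courses". For the next round of the same regimens, its wording is "and d.1 only during the second cycles of CHOD-Bleo and NOPP".

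Scenarios A to C then list the courses one by one. Scenario A covers patients whose bcl-2 status is known before treatment, and it includes "course 4: CHOD-Bleo, plus rituximab d.1 only". Scenario B covers patients who have already had FND with rituximab, and it includes "course 5: CHOD-Bleo without rituximab". Scenario C covers patients who have had FND without rituximab. All three stop rituximab before courses 7-9.

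For the Scenario B patients, Part I also says that the later ATT courses, "with d.1 and 8 IDEC during each CHOD-Bleo and NOPP course, should complete all 6 planned doses of rituximab", and it points to Scenario B.

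Just before Part II, the text says that in cycles given with rituximab the steroid starts on day 1 and the rest of the chemotherapy starts a day later than usual. Part II follows under the heading "II. ATT doses and schedule (with rituximab in CHOD-Bleo and NOPP courses". Its CHOD-Bleo and NOPP tables show rituximab on days 1 and 8, a course total of 750 mg/m2, and chemotherapy from day 2. Neither table names the courses it covers or refers back to the scenarios.

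**The concern.** The sentence for crossover patients states a rule and a total that cannot both hold over the courses in Scenario B. Separately, the Part II tables are the only place where the ATT agents, doses and days are set out together. Someone writing orders from them would find two rituximab doses per course and chemotherapy from day 2, with nothing to show that some CHOD-Bleo and NOPP courses differ.

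Two readers could therefore write different orders for the same patient, both in the number of antibody doses and in the chemotherapy days. That is a patient-safety matter first. It also bears on interpretation: treating germline patients by a separate strategy is objective 1.4, and section 10.4 d reports them mainly descriptively. If orders varied, the report would describe a mixture of regimens.

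**Working it through.** **Inputs.** The dose is 375 mg/m2 per administration (section 5.4.1). The stated total is 6 doses (Appendix B, Part I), or 6 × 375 = 2250 mg/m2. The CHOD-Bleo and NOPP courses, counted from the scenario lists, are:

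- Scenario A: courses 1, 3, 4, 6, 7 and 9 (six courses).
- Scenarios B and C: courses 2, 4, 5, 7 and 8 (five courses each), after one FND course.

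**The plan's own figure.** The Part I rule gives 2 + 2 in the first CHOD-Bleo and NOPP and 1 + 1 in the second, which is 6. The scenario lists also give 6 each (first column below).

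**The crossover sentence.** Two doses with FND, then days 1 and 8 in each of Scenario B's five CHOD-Bleo and NOPP courses, gives 2 + 5 × 2 = 12. Scenario B reaches six by giving rituximab only in courses 2 and 4: 2 (FND) + 2 + 2 = 6.

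**The tables at their widest.** Formula: doses given with FND + 2 × the number of CHOD-Bleo and NOPP courses. The last column repeats this but keeps the scenarios' instruction to give none in courses 7-9.

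| Scenario | As listed | Days 1 and 8 in every CHOD-Bleo and NOPP course | Same, none in courses 7-9 |
|---|---|---|---|
| A | 2 + 2 + 1 + 1 = 6 | 6 × 2 = 12 (4500 mg/m2; 2.0 times) | 4 × 2 = 8 |
| B | 2 + 2 + 2 = 6 | 2 + 5 × 2 = 12 (4500 mg/m2; 2.0 times) | 2 + 3 × 2 = 8 |
| C | 2 + 2 + 2 = 6 | 5 × 2 = 10 (3750 mg/m2; 1.67 times) | 3 × 2 = 6 |

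**Courses that the printed tables do not fit.** By the scenario lists, rituximab is on day 1 only in courses 4 and 6 of A, so the printed 750 mg/m2 does not apply there. There is no rituximab in CHOD-Bleo or NOPP courses 7 and 9 (A), 5, 7 and 8 (B), and 7 and 8 (C). For these, neither the rituximab row nor the day-2 start applies, because the text limits the shift to cycles given with rituximab.

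**Placement of the six doses.** The totals agree but the distribution does not. The Part I rule puts one dose in each second cycle. Scenario C puts two in the second CHOD-Bleo (course 5) and none in the second NOPP (course 7). Scenario B puts none in either.

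**The case against.** The strongest reply is that the plan is clear enough. Part I states six doses, every scenario adds up to six, and no passage states a higher total. The crossover sentence covers one subgroup, carries its own six-dose total and sends the reader to Scenario B. The tables never say that they apply to every course; they are labelled as initial regimens, and days 1 and 8 are right for the first CHOD-Bleo and first NOPP in all three scenarios. The days without rituximab can be worked out from the stated one-day shift. The appendix also tells readers to ask the principal investigator about the sequence.

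Much of this stands. A reader might infer that Appendix B sets out two rival schedules, or that it prescribes up to twice the stated antibody dose. The documents do not support that. Reaching 12 doses from the tables means ignoring the day-1-only entries, the course marked as having no rituximab, and the stop before courses 7-9. A reader might also infer that the tables misstate the chemotherapy days. They do not: they print the days for cycles with rituximab and leave the other days to be inferred.

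Two parts of the reply do not stand. A six-dose total does not rescue the crossover sentence, because its rule and its total conflict over Scenario B's five courses. And the label most naturally means starting dose level, not first course. The ESHAP table carries the same label and is the only ESHAP table for all three ESHAP courses. The doses also match level 0 in Part III (for example Adriamycin 50, Cytoxan 750, etoposide 40, cisplatin 25, Novantrone 10 and procarbazine 100 mg/m2). The option to consult helps only someone who has noticed the conflict.

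**Conclusion.** The point holds as an internal inconsistency. The six-dose total is stated and reproduced, but the crossover sentence contradicts Scenario B (12 doses against 6 if followed literally), and the Part II tables do not say which courses they cover. The figures of 12, 12 and 10 are a worst case that assumes the tables are applied to every CHOD-Bleo and NOPP course and the scenario lists are set aside. With rituximab withheld in courses 7-9 they fall to 8, 8 and 6, so Scenario C then shows no excess. Nothing in the documents shows what was actually ordered, so these counts describe readings of the text, not doses given.

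The reach is limited to the germline group: about 15% of follicular patients, or about 16 on the earlier trial according to section 10.4 d. The primary comparison and the sample size are unaffected. It still deserves correction, because a stated dosing rule disagrees with its own schedule.

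**What to change.** The sponsor should reconcile four things in Appendix B into one consistent course-by-course schedule: the crossover sentence, the general rule in Part I, Scenarios A to C, and the Part II tables. Each table should then state which courses its rituximab row covers and which courses its chemotherapy days cover, so that courses with two doses, one dose or none can each be ordered without inference. Section 5.3 already separates course 1, courses 2-5 and courses 6-8 for Arm 2 and is a model for the layout. Which schedule is intended is for the sponsor to decide; none is preferred here.

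The cost is a wording amendment to one appendix, with no extra patients, tests or visits.

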## 5.6 Dose Modification Guidelines

### 5.6.1 Recommended Guidelines for Hematological Toxicity

Lowest granulocyte	Lowest platelet	Modification
> 1000 and	>100,000	Increase one level
>200 but <1000 or <200 for ≥ days	>20,000 but <100,000	No change
<200 for > 5 days and/or	<20,000	Decrease one level
Documented infection with neutropenia	Mucosal bleeding	Decrease one level

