#### 10.4 Other Statistical Considerations

- a) Another secondary aim is to compare response rates, both CR (clinical CR plus CRu -- see Section 8.2) and CR + PR. It is anticipated to be high (approximately 80% CR and >90% CR + PR) in both arms; therefore it is unlikely that there will be significant differences between arms.
- b) Molecular response rates will be compared to CR and CR + PR rates.
- c) Other secondary aims, which are to compare the 5 year disease-free survival and overall survival for these 2 treatments, and to correlate the molecular complete remission rate with these endpoints, will require longer follow up. To attain these goals, we will follow the patients for at least 5 years to determine if a difference develops in disease-free survival. It might take 10 years or more of follow-up to establish statistically significant survival trends.
- d) Patients who are PCR negative will also be entered in this trial. These are of 2 categories: (a) "germline" follicular lymphoma; and (b) DSL (i.e., not follicular lymphoma).

Our preliminary data indicates that "germline" follicular patients have not done as well with FND as with ATT, so they will receive ATT, with rituximab. This will be a small number of patients (about 15% of follicular patients, i.e., about 16 patients on DM92-103), for whom analysis will be mainly descriptive. Likewise for DSL, which also will be a small subset of patients (24 in 4 1/2 years on DM92-103), traditional endpoints, including CR, PR, FFS, and survival will be used.

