#### IV. Recommended Dose Modification Guidelines

1. For Hematologic Toxicity -- see Section 5.6
2. For Renal Toxicity

Serum Creatinine (mg%)		Creatinine Clearance (cc/min)	Modification of Cisplatin
0.6 - 1.4	or	> 75	None
1.5 - 2.0	or	60 - 74	33% reduction
2.1 - 2.5	or	40 - 59	50% reduction
>2.5 - 4.0	or	<39	Delete*

\* Cisplatin could be given at 25% dose, after consultation with Study Chairman, if renal failure is secondary to lymphoma.

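### Two of the four Ara-C doses in the Appendix B ESHAP dose-level table are in mg/m² where g/m² must be meant

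*Combined protocol and SAP*

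**What the plan says.** Appendix B, II.2 sets the initial ESHAP regimen. Its Ara-C row reads "Ara-C 1.5 gm/m 2 (single dose) 5 IV 2 hrs 1.5 gm/m 2", so 1.5 g/m² is given both as the dose and as the total dose.

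Appendix B, III.2 lists the ESHAP dose levels for myelotoxicity. Its Ara-C row, for levels -2, -1, 0 and +1, reads "Ara-C x1 0.5 mg/m 2 1 g/m 2 1.5 mg/m 2 2 g/m 2".

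Appendix B, IV.1 says "For Hematologic Toxicity -- see Section 5.6". The table in Section 5.6.1 then gives "Decrease one level" for severe or prolonged low counts, neutropenic infection or mucosal bleeding, and "Increase one level" when nadirs stay high.

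The row applies to follicular lymphoma patients without bcl-2 rearrangement, who receive ATT. Section 10.4 d) puts them at "about 15% of follicular patients, i.e., about 16 patients on DM92-103", "for whom analysis will be mainly descriptive".

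**The concern.** A dose-level row should rise from level -2 to level +1, and level 0 should equal the starting dose. This row does neither.

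The two faulty cells differ in how far the rest of the protocol can correct them. A reader who doubts level 0 can go back to II.2. A reader who doubts level -2 has only the pattern of the row to go by.

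Section 5.6.1 speaks only of moving a level, and the table in III.2 is the only place where those levels are defined for ESHAP. Followed literally, it would almost remove Ara-C from the regimen of a patient reduced twice. It would do the same for a patient whose level 0 dose is read from the table on re-escalation. These patients are assigned ATT because they appeared to do worse on FND, so losing an ESHAP component works against the reason for treating them separately.

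**Working it through.** **Inputs.** The starting dose is 1.5 g/m² = 1,500 mg/m² (Appendix B, II.2). The dose levels are from Appendix B, III. The course order is from the Appendix B scenarios.

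**Ara-C row in one unit (mg/m²)**

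| Level | As printed | With g/m² in all cells | Corrected, as % of level 0 |
|---|---|---|---|
| -2 | 0.5 | 500 | 500/1,500 = 33% |
| -1 | 1,000 | 1,000 | 1,000/1,500 = 67% |
| 0 | 1.5 | 1,500 | 100% |
| +1 | 2,000 | 2,000 | 2,000/1,500 = 133% |

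- Level 0 against the starting dose: 1,500 / 1.5 = 1,000.
- Level -2 against level -1, as printed: 0.5 / 1,000 = 1/2,000. Corrected: 500 / 1,000 = 1/2.
- Level -2 against the starting dose, as printed: 0.5 / 1,500 = 1/3,000 = 0.033%.
- The printed row is not in order, because level 0 (1.5) lies below level -1 (1,000). The corrected row rises in equal steps of 500 mg/m², and its level 0 equals the starting dose.

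**Other rows.** The remaining 12 level 0 entries in the three Appendix B tables (five CHOD-Bleo, three ESHAP, four NOPP) all match their initial dosing tables. Ara-C is the only mismatch.

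**Level -2 as a share of level 0, for the six other drugs that are reduced**

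- Etoposide: 25/40 = 62.5%
- Cisplatin: 16/25 = 64%
- Adriamycin: 35/50 = 70%
- Cyclophosphamide: 500/750 = 66.7%
- Novantrone: 6/10 = 60%
- Procarbazine: 60/100 = 60%

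**How many ESHAP courses could be at level -2.** ESHAP is given at courses 2, 5 and 8 (scenario A) or 3, 6 and 9 (scenarios B and C). Level -2 needs two reductions. The plan does not say whether a level carries over between regimens, so the following are assumptions:

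- Levels kept per regimen: ESHAP runs 0, -1, -2, so at most 1 of 3 courses (course 8 or 9).
- Levels carried across the ATT regimens: CHOD-Bleo 0, ESHAP -1, NOPP -2, so up to 2 of 3 (from course 5 in A, course 6 in B and C).
- Levels also carried over from FND in B and C: FND 0, CHOD-Bleo -1, ESHAP -2, so up to 3 of 3 (from course 3).

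These course numbers assume at most one FND cycle before crossover. Appendix B allows two in rare cases, which shifts them.

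**The case against.** The strongest objection is that the intended values are obvious. The row cannot be read as an ascending scale, II.2 settles level 0, and 0.5, 1, 1.5, 2 g/m² suggests itself at once. If levels are kept per regimen, a patient reaching level -2 has already received 1.5 g/m² and then 1 g/m², so 0.5 mg/m² would contradict that patient's own record. The same record would normally protect a patient re-escalated to level 0. The rules that lead to the table are headed as recommendations, the group is small, and two reductions are needed.

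All of this lowers the chance of harm, but it does not make the row correct. For level -2 the safeguard is the pattern of the row or a clinician's suspicion, not a figure in the protocol. If levels carry over between regimens, a patient could reach ESHAP level -2 without having stepped through ESHAP at levels 0 and -1.

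A second objection is that the fault may lie in the PDF text, with gm misread as mg. If the source mixes g and gm, such a misread would hit exactly the gm cells, so the fact that the faulty cells are not adjacent is only weak evidence against it. On the other side, gm is read correctly twice in II.2, and the neighbouring rows are intact. The possibility remains, and it is why the source page should be checked first.

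A third is that nothing obliges Ara-C to be cut in the same proportion as the other drugs. That is right. The 60% to 70% comparison does not show that 0.5 g/m² is wrong. It only explains why that value needs confirming.

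**Conclusion.** The concern holds. As printed, level 0 is too low by a factor of 1,000 against the protocol's own starting dose. Level -2 is too low by the same factor if 0.5 g/m² was meant, and no other entry corrects it. It is a unit error in a table that governs cytotoxic dosing; no calculation in the statistical section is wrong.

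The reach is limited. First ESHAP doses come from the correct entry in II.2, and levels -1 and +1 are printed sensibly. Only germline patients on ATT are exposed, including those crossed over from FND. The documents do not say how many would reach level -2. The randomized comparison, its sample size and its power are not affected.

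The conclusion assumes that the source page carries the same units as the text.

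**What to change.** Check the source page. If it shows the same units, change the level -2 and level 0 cells to g/m², so that the row reads 0.5, 1, 1.5 and 2 g/m². Ask the clinical team to confirm the four values, level -2 in particular: it is inferred only from the step pattern, and at 33% of the starting dose it is a deeper cut than for the other drugs.

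The cost is two cells in one row, by amendment or clarification memo.

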#### IV. Recommended Dose Modification Guidelines

1. For Hematologic Toxicity -- see Section 5.6
2. For Renal Toxicity

Serum Creatinine (mg%)		Creatinine Clearance (cc/min)	Modification of Cisplatin
0.6 - 1.4	or	> 75	None
1.5 - 2.0	or	60 - 74	33% reduction
2.1 - 2.5	or	40 - 59	50% reduction
>2.5 - 4.0	or	<39	Delete*

\* Cisplatin could be given at 25% dose, after consultation with Study Chairman, if renal failure is secondary to lymphoma.

APPENDIX C

PERFORMANCE STATUS SCALES

Karnofsky Performance Scale (1)		Zubrod Performance Scale (2)	
Point	Description	Point	Description
100	Normal, no complaints, no evidence of disease	0	Normal activity; asymptomatic
90	Able to carry on normal activity; minor signs or symptoms of disease	1	Symptomatic; but ambulatory
80	Normal activity with effort; some signs or symptoms of disease		
70	Cares for self, unable to carry on normal activity or to do active work	2	Symptomatic; in bed 50% of time
60	Requires occasional assistance, but able to care for most of own needs		
50	Requires considerable assistance and frequent medical care	3	Symptomatic; in bed 50% of time; not bedridden
40	Disabled, requires special care and assistance		
30	Severely disabled, hospitalization indicated. Death not imminent	4	100% bedridden
20	Very sick, hospitalization indicated. Death not imminent		
10	Moribund, fatal processes, progressing rapidly		
0	Dead	5	Dead

REFERENCES

1. Karnofsky, D.A: Meaningful Clinical Classification of Therapeutic Responses to Anti-Cancer Drugs. Editorial. Clin. Pharmacol and Therapeutics 2:709-712, 1961.
2. Stanley, K.E.: Prognostic Factors for Survival in Patients with Inoperable Lung Cancer. J. Natl. Can. Inst. 65:25-32, 1980.

APPENDIX D

NCI COMMON TOXICITY CRITERIA

Toxicity	Grade				
	0	1	2	3	4
ALLERGY/IMMUNOLOGY					
Allergic reaction/ hypersensitivity (including drug fever)	none	transient rash, drug fever < 38°C (<100.4°F)	urticaria, drug fever ≥ 38°C (≥100.4°F), and/or asymptomatic bronchospasm	symptomatic bronchospasm, requiring parenteral medication(s), with or without urticaria; allergy- related edema/angioede ma	anaphylaxis
Note: Isolated urticaria, in the absence of other manifestations of an allergic or hypersensitivity reaction, is graded in the DERMATOLOGY/SKIN category.					
Allergic rhinitis (including sneezing, nasal stuffiness, postnasal drip)	none	mild, not requiring treatment	moderate, requiring treatment	-	-
Autoimmune reaction	none	serologic or other evidence of autoimmune reaction but patient is asymptomatic (e.g., vitiligo), all organ function is normal and no treatment is required	evidence of autoimmune reaction involving a non- essential organ or function (e.g., hypothyroidism), requiring treatment other than immunosuppress ive drugs	reversible autoimmune reaction involving function of a major organ or other toxicity (e.g., transient colitis or anemia), requiring short- term immunosuppress ive treatment	autoimmun e reaction causing major grade 4 organ dysfunction; progressive and irreversible reaction; long-term administrati on of high- dose immuno- suppressive therapy required
Also consider Hypothyroidism, Colitis, Hemoglobin, Hemolysis.					
Serum sickness	none	-	-	present	-
Urticaria is graded in the DERMATOLOGY/SKIN category if it occurs as an isolated symptom. If it occurs with other manifestations of allergic or hypersensitivity reaction, grade as Allergic reaction/hypersensitivity above.					
Vasculitis	none	mild, not requiring treatment	symptomatic, requiring medication	requiring steroids	ischemic changes or requiring amputation
Allergy/Immunolog y-Other (Specify, _____)	none	mild	moderate	severe	life- threatening or disabling
AUDITORY/HEARING					
Conductive hearing loss is graded as Middle ear/hearing in the AUDITORY/HEARING category.					

Toxicity	Grade				
	0	1	2	3	4
Earache is graded in the PAIN category.					
External auditory canal	normal	external otitis with erythema or dry desquamation	external otitis with moist desquamation	external otitis with discharge, mastoiditis	necrosis of the canal soft tissue or bone
Note: Changes associated with radiation to external ear (pinnae) are graded under Radiation dermatitis in the DERMATOLOGY/SKIN category.					
Inner ear/hearing	normal	hearing loss on audiometry only	tinnitus or hearing loss, not requiring hearing aid or treatment	tinnitus or hearing loss, correctable with hearing aid or treatment	severe unilateral or bilateral hearing loss (deafness), not correctable
Middle ear/hearing	normal	serous otitis without subjective decrease in hearing	serous otitis or infection requiring medical intervention; subjective decrease in hearing; rupture of tympanic membrane with discharge	otitis with discharge, mastoiditis or conductive hearing loss	necrosis of the canal soft tissue or bone
Auditory/Hearing-Other (Specify, _____)	normal	mild	moderate	severe	life-threatening or disabling
BLOOD/BONE MARROW					
Bone marrow cellularity	normal for age	mildly hypocellular or 25% reduction from normal cellularity for age	moderately hypocellular or >25 - ≤ 50% reduction from normal cellularity for age or >2 but <4 weeks to recovery of normal bone marrow cellularity	severely hypocellular or >50 - ≤ 75% reduction in cellularity for age or 4 - 6 weeks to recovery of normal bone marrow cellularity	aplasia or >6 weeks to recovery of normal bone marrow cellularity
Normal ranges:					
children (≤ 18 years)	90% cellularity average				
younger adults (19-59)	60-70% cellularity average				
older adults (≥ 60 years)	50% cellularity average				
Note: Grade Bone marrow cellularity only for changes related to treatment not disease.					
CD4 count	WNL	< LLN - 500/mm 	200 - < 500/mm 	50 - < 200/mm 	< 50/mm 

Toxicity	Grade				
	0	1	2	3	4
Haptoglobin	normal	decreased	-	absent	-
Hemoglobin (Hgb)	WNL	< LLN - 10.0 g/dl < LLN - 100 g/L < LLN - 6.2 mmol/L	8.0 - < 10.0 g/dl 80 - < 100 g/L 4.9 - < 6.2 mmol/L	6.5 - < 8.0 g/dl 65 - 80 g/L 4.0 - < 4.9 mmol/L	< 6.5 g/dl < 65 g/L < 4.0 mmol/L
Note: The following criteria may be used for leukemia studies or bone marrow infiltrative/myelophthisic process if the protocol so specifies.					
For leukemia studies or bone marrow infiltrative/myelophthisic processes	WNL	10 - <25% decrease from pretreatment	25 - <50% decrease from pretreatment	50 - <75% decrease from pretreatment	≥75% decrease from pretreatment
Hemolysis (e.g., immune hemolytic anemia, drug-related hemolysis, other)	none	only laboratory evidence of hemolysis [e.g., direct antiglobulin test (DAT, Coombs') schistocytes]	evidence of red cell destruction and ≥ 2gm decrease in hemoglobin, no transfusion	requiring transfusion and/or medical intervention (e.g., steroids)	catastrophic consequences of hemolysis (e.g., renal failure, hypotension, bronchospasm, emergency splenectomy)
Also consider Haptoglobin, Hgb.					
Leukocytes (total WBC)	WNL	< LLN - $3.0 \times 10^9$ /L < LLN - 3000/mm 	≥2.0 - < $3.0 \times 10^9$ /L ≥2000 - < 3000/mm 	≥1.0 - < $2.0 \times 10^9$ /L ≥1000 - < 2000/mm 	< $1.0 \times 10^9$ /L < 1000/mm 
For BMT studies:	WNL	≥2.0 - < $3.0 \times 10^9$ /L ≥2000 - < 3000/mm 	≥1.0 - < $2.0 \times 10^9$ /L ≥1000 - < 2000/mm 	≥0.5 - < $1.0 \times 10^9$ /L ≥500 - < 1000/mm 	< $0.5 \times 10^9$ /L < 500/mm 
Note: The following criteria using age, race and sex normal values may be used for pediatric studies if the protocol so specifies.					
Lymphopenia	WNL	≥75 - <100% LLN <LLN - $1.0 \times 10^9$ /L <LLN - 1000/mm 	≥50 - <75% LLN ≥0.5 - < $1.0 \times 10^9$ /L ≥500 - < 1000/mm 	≥25 - 50% LLN < $0.5 \times 10^9$ /L < 500/mm 	<25% LLN
Note: The following criteria using age, race, and sex normal values may be used for pediatric studies if the protocol so specifies.					
Neutrophils/granulocytes (ANC/AGC)	WNL	≥75 - <100% LLN ≥1.5 - < $2.0 \times 10^9$ /L ≥1500 - < 2000/mm 	≥50 - <75% LLN ≥1.0 - < $1.5 \times 10^9$ /L ≥1000 - < 1500/mm 	≥25 - <50% LLN ≥0.5 - < $1.0 \times 10^9$ /L ≥500 - < 1000/mm 	<25% LLN < $0.5 \times 10^9$ /L < 500/mm 
For BMT:	WNL	≥1.0 - < $1.5 \times 10^9$ /L ≥1000 - < 1500/mm 	≥0.5 - < $1.0 \times 10^9$ /L ≥500 - < 1000/mm 	≥0.1 - < $0.5 \times 10^9$ /L ≥100 - < 500/mm 	< $0.1 \times 10^9$ /L < 100/mm 
Note: The following criteria may be used for leukemia studies or bone marrow infiltrative/myelophthisic process if the protocol so specifies.					

Toxicity	Grade				
	0	1	2	3	4
For leukemia studies or bone marrow infiltrative/myelophthisic process	WNL	10 - <25% decrease from baseline	25 - <50% decrease from baseline	50 - <75% decrease from baseline	≥75% decrease from baseline
Platelets	WNL	< LLN - <75.0 x 10  /L	≥50.0 - < 75.0 x 10  /L	≥10.0 - < 50.0 x 10  /L	< 10.0 x 10  /L
For BMT:	WNL	< LLN - 75000/mm 	≥50000 - < 75000/mm 	≥10000 - < 50000/mm 	< 10000/mm 
		≥50.0 - <75.0 x 10  /L	≥20.0 - <50.0 x 10  /L	≥10.0 - <20.0 x 10  /L	<10.0 x 10  /L
		≥50000 - <75000/mm 	≥20000 - <50000/mm 	≥10000 - <20000/mm 	<10000/mm 
Note: The following criteria may be used for leukemia studies or bone marrow infiltrative/myelophthisic process if the protocol so specifies.					
For leukemia studies or bone marrow infiltrative/myelophthisic process	WNL	10 - <25% decrease from baseline	25 - <50% decrease from baseline	50 - <75% decrease from baseline	≥75% decrease from baseline
Transfusion: Platelets	none	-	-	yes	platelet transfusions and other measures required to improve platelet increment; platelet transfusion refractoriness associated with life-threatening bleeding. (e.g., HLA or cross matched platelet transfusions )

	Grade				
Toxicity	0	1	2	3	4
For BMT:	none	1 platelet transfusion in 24 hours	2 platelet transfusions in 24 hours	≥3 platelet transfusions in 24 hours	platelet transfusions and other measures required to improve platelet increment; platelet transfusion refractoriness associated with life-threatening bleeding. (e.g., HLA or cross matched platelet transfusions.)
Also consider Platelets.					
Transfusion: pRBCs For BMT:	none none	- ≤2 u pRBC (≤15cc/kg) in 24 hours elective or planned	- 3 u pRBC (>15 ≤30cc/kg) in 24 hours elective or planned	Yes ≥4 u pRBC (>30cc/kg) in 24 hours	hemorrhage or hemolysis associated with life-threatening anemia; medical intervention required to improve hemoglobin
Also consider Hemoglobin.					
Blood/Bone Marrow-Other (Specify, _____)	none	mild	moderate	severe	life-threatening or disabling
CARDIOVASCULAR (ARRHYTHMIA)					
Conduction abnormality/ Atrioventricular heart block	none	asymptomatic, not requiring treatment (e.g., Mobitz type I second-degree AV block, Wenckebach)	symptomatic, but not requiring treatment	symptomatic and requiring treatment (e.g., Mobitz type II second-degree AV block, third-degree AV block)	life-threatening (e.g., arrhythmia associated with CHF, hypotension, syncope, shock)

Toxicity	Grade				
	0	1	2	3	4
Nodal/junctional arrhythmia/dysrhythmia	none	asymptomatic, not requiring treatment	symptomatic, but not requiring treatment	symptomatic and requiring treatment	life-threatening (e.g., arrhythmia associated with CHF, hypotension, syncope, shock)
Palpitations Note: Grade palpitations only in the absence of a documented arrhythmia.	none	present	-	-	-
Prolonged QTc interval (QTc > 0.48 seconds)	none	asymptomatic, not requiring treatment	symptomatic, but not requiring treatment	symptomatic and requiring treatment	life-threatening (e.g., arrhythmia associated with CHF, hypotension, syncope, shock)
Sinus bradycardia	none	asymptomatic, not requiring treatment	symptomatic, but not requiring treatment	symptomatic and requiring treatment	life-threatening (e.g., arrhythmia associated with CHF, hypotension, syncope, shock)
Sinus tachycardia	none	asymptomatic, not requiring treatment	symptomatic, but not requiring treatment	symptomatic and requiring treatment of underlying cause	-
Supraventricular arrhythmias (SVT/atrial fibrillation/ flutter)	none	asymptomatic, not requiring treatment	symptomatic, but not requiring treatment	symptomatic and requiring treatment	life-threatening (e.g., arrhythmia associated with CHF, hypotension, syncope, shock)
Syncope (fainting) is graded in the NEUROLOGY category.					
Vasovagal episode	none	-	present without loss of consciousness	present with loss of consciousness	-

Toxicity	Grade				
	0	1	2	3	4
Ventricular arrhythmia (PVCs/bigeminy/trigeminy/ventricular tachycardia)	none	asymptomatic, not requiring treatment	symptomatic, but not requiring treatment	symptomatic and requiring treatment	life-threatening (e.g., arrhythmia associated with CHF, hypotension, syncope, shock)
Cardiovascular/Arrhythmia-Other (Specify, _____)	none	asymptomatic, not requiring treatment	symptomatic, but not requiring treatment	symptomatic, and requiring treatment of underlying cause	life-threatening (e.g., arrhythmia associated with CHF, hypotension, syncope, shock)
CARDIOVASCULAR (GENERAL)					
Acute vascular leak syndrome	absent	-	symptomatic, but not requiring fluid support	respiratory compromise or requiring fluids	life-threatening; requiring pressor support and/or ventilatory support
Cardiac-ischemia/infarction	none	non-specific T-wave flattening or changes	asymptomatic, ST- and T- wave changes suggesting ischemia	angina without evidence of infarction	acute myocardial infarction
Cardiac left ventricular function	normal	asymptomatic decline of resting ejection fraction of $\geq 10\%$ but $< 20\%$ of baseline value; shortening fraction $\geq 24\%$ but $< 30\%$	asymptomatic but resting ejection fraction below LLN for laboratory or decline of resting ejection fraction $\geq 20\%$ of baseline value; $< 24\%$ shortening fraction	CHF responsive to treatment	severe or refractory CHF or requiring intubation
CNS cerebrovascular ischemia is graded in the NEUROLOGY category.					
Cardiac troponin I (cTnI)	normal	-	-	levels consistent with unstable angina as defined by the manufacturer	levels consistent with myocardial infarction as defined by the manufacturer
Cardiac troponin T (cTnT)	normal	$\geq 0.03$ - $< 0.05$ ng/ml	$\geq 0.05$ - $< 0.1$ ng/ml	$\geq 0.1$ - $< 0.2$ ng/ml	$\geq 0.2$ ng/ml

Toxicity	Grade				
	0	1	2	3	4
Edema	none	asymptomatic, not requiring therapy	symptomatic, requiring therapy	symptomatic edema limiting function and unresponsive to therapy or requiring drug discontinuation	anasarca (severe generalized edema)
Hypertension	none	asymptomatic, transient increase by >20 mmHg (diastolic) or to > 150/100* if previously WNL; not requiring treatment	recurrent or persistent or symptomatic increase by > 20 mmHg (diastolic) or to > 150/100* if previously WNL; not requiring treatment	requiring therapy or more intensive therapy than previously	hypertensive crisis
*Note: For pediatric patients, use age and sex appropriate normal values > 95th percentile ULN.					
Hypotension	none	changes, but not requiring therapy (including transient orthostatic hypotension)	requiring brief fluid replacement or other therapy but not hospitalization; no physiologic consequences	requiring therapy and sustained medical attention, but resolves without persisting physiologic consequences	shock (associated with acidemia and impairing vital organ function due to tissue hypoperfusion)
Also consider Syncope (fainting). Note: Angina or MI is graded as Cardiac- ischemia/infarction in the CARDIOVASCULAR (GENERAL) category. For pediatric patients, systolic BP 65 mmHg or less in infants up to 1 year old and 70 mmHg or less in children older than 1 year of age, use two successive or three measurements in 24 hours.					
Myocarditis	none	-	-	CHF responsive to treatment	severe or refractory CHF
Operative injury of vein/artery	none	primary suture repair for injury, but not requiring transfusion	primary suture repair for injury, requiring transfusion	vascular occlusion requiring surgery or bypass for injury	myocardial infarction; resection of organ (e.g., bowel, limb)
Pericardial effusion/pericarditis	none	asymptomatic effusion, not requiring treatment	pericarditis (rub, ECG changes, and/or chest pain)	physiologic consequences resulting from symptoms	tamponade (drainage or pericardial window required)
Peripheral arterial ischemia	none	-	brief episode of ischemia managed non-surgically and without permanent deficit	requiring surgical intervention	life-threatening or with permanent functional deficit (e.g., amputation)

Toxicity	Grade				
	0	1	2	3	4
Phlebitis (superficial) Note: Injection site reaction is graded in the DERMATOLOGY/SKIN category. Thrombosis/embolism is graded in the CARDIOVASCULAR (GENERAL) category.	none	-	present	-	-
Syncope (fainting) is graded in the NEUROLOGY category.					
Thrombosis/embolism	none	-	deep vein thrombosis, not requiring anticoagulant	deep vein thrombosis, requiring anticoagulant therapy	embolic event including pulmonary embolism
Vein/artery operative injury is graded as Operative injury of vein/artery in the CARDIOVASCULAR (GENERAL) category.					
Visceral arterial ischemia (non-myocardial)	none	-	brief episode of ischemia managed non-surgically and without permanent deficit	requiring surgical intervention	life-threatening or with permanent functional deficit (e.g., resection of ileum)
Cardiovascular/General-Other (Specify, _____)	none	mild	moderate	severe	life-threatening or disabling
COAGULATION					
Note: See the HEMORRHAGE category for grading the severity of bleeding events.					
DIC (disseminated intravascular coagulation) Also grade Platelets. Note: Must have increased fibrin split products or D-dimer in order to grade as DIC.	absent	-	-	laboratory findings present with no bleeding	laboratory findings and bleeding
Fibrinogen	WNL	≥0.75 - <1.0 x LLN	≥0.5 - <0.75 x LLN	≥0.25 - <0.5 x LLN	<0.25 x LLN
Note: The following criteria may be used for leukemia studies or bone marrow infiltrative/myelophthitic process if the protocol so specifies.					
For leukemia studies:	WNL	<20% decrease from pretreatment value or LLN	≥20 - <40% decrease from pretreatment value or LLN	≥40 - <70% decrease from pretreatment value or LLN	<50 mg%
